1. LIST OF ABBREVIATIONS

ACT	Artemisinin-based combination therapy
AE	Adverse event
AL	Artemether-Lumefantrine
AQ	Amodiaquine
AS	Artesunate
ASAQ	Artesunate-Amodiaquine
AUC	Area under the curve
CBC	Complete Blood Count
CRF	Case report form
DNA	Deoxyribonucleic acid
DP	Dihydroartemisinin-Piperaquine
DSMB	Data and Safety Monitoring Board
EC	Ethics Committee
EDTA	Ethylenediaminetetraacetic acid
G6PD	Glucose-6-phosphatase dehydrogenase
GCP	Good clinical practice
Hb	Haemoglobin
Hct	Haematocrit
LSHTM	London School of Hygiene and Tropical Medicine
MACS	Magnetic-activated cell sorting
MFA	Membrane feeding assay
MRTC	Malaria Research and Training Centre (Bamako, Mali)
P. falciparum	Plasmodium falciparum
PA	Pyronaridine-Artesunate
PCR	Polymerase chain reaction
PQ	Primaquine
RBCs	Red blood cells
RT-qPCR	Quantitative reverse transcriptase polymerase chain reaction
SAE	Serious Adverse Event
SLD	Single low dose
SOP	Standard operating procedure
SUSAR	Serious and Unexpected Suspected Adverse Reaction
TACT	Triple Artemisinin-based Combination Therapy
UP	Unanticipated Problem
UPnonAE	Unanticipated Problem that is not an Adverse Event
WHO	World Health Organisation

2. STUDY SYNOPSIS

Artemisinin Combination Therapies (ACT) are the first-line treatment for uncomplicated *Plasmodium falciparum* malaria. ACTs rapidly clear asexual *P. falciparum* parasites, responsible for clinical symptoms, but have limited activity against mature gametocytes, which are the only life stages capable of transmitting to mosquitoes. To reduce *P. falciparum* transmission, the World Health Organisation (WHO) recommends the addition of a single low dose of primaquine (0.25 mg/kg), a potent and fast-acting gametocytocidal drug, to ACT [1]. Although Artesunate-Amodiaquine (ASAQ) is a commonly used ACT, limited available data

suggest poor activity against gametocytes [2] and the added benefit of SLD PQ in combination with ASAQ remains unknown. We previously showed that Artemether-Lumefantrine (AL) is a more potent ACT in terms of gametocyte clearance and transmission reduction efficacy compared to Dihydroartemisinin-Piperaquine (DP) [3], [4] [NECTAR3, in preparation]. Recently, triple artemisinin-based combination therapies (TACT) such as Artemether-Lumefantrine plus Amodiaquine (ALAQ) have been proposed to delay the emergence of drug resistance and to provide efficacious treatment for multi-drug resistance *P. falciparum* infections [5], [6]. The transmission reducing efficacy of ALAQ or ALAQ-PQ has not yet been tested.

In this study we aim to determine transmission reducing efficacy of Artesunate-Amodiaquine (ASAQ) with and without a single low dose (0.25mg/kg) of Primaquine (SLD PQ) and Artemether-Lumefantrine (AL) with and without Amodiaquine (AQ) and Primaquine (PQ). To achieve this, we propose to conduct a five-arm, single-blind, randomised control trial to test the gametocytocidal and transmission-blocking efficacy of SLD PQ in combination with Artesunate-Amodiaquine and Artemether-Lumefantrine-Amodiaquine. Individuals will be recruited to an AL-only arm as an internal control for the ALAQ arm, and for comparison to recent trials at the same site [NECTAR3, in preparation]. Individuals who meet inclusion criteria will be randomised in a 1:1:1:1:1 ratio to: ASAQ, ASAQ-PQ, AL, ALAQ, ALAQ-PQ.

For participation in the trial, individuals between 10-50 years will be recruited from villages around Ouelessebougou, near Bamako in Mali. Written, informed consent will be obtained. Inclusion criteria include presence of ≥ 16 gametocytes/ μL , absence of other non-*P. falciparum* species on blood film, absence of symptomatic falciparum malaria, haemoglobin ≥ 10 g/dL, and no evidence of acute severe or chronic disease or pregnancy. Recruitment will continue until 100 individuals who meet the inclusion criteria are recruited and randomised. G6PD enzyme status will not be tested.

Participants will be followed for 28 days. Blood samples will be taken pre-treatment, and at days 2, 7, 14, 21 and 28 post-treatment for parasitology, genetic, haematology and biochemistry analysis. MFA will be conducted pre-treatment, and at days 2, 7 and 14 post-treatment. MFA will also be conducted at day 21 for any individuals infectious at day 7 or 14; and at day 28 for any individuals infectious at day 14 or 21. Magnetic-activated cell sorting (MACS) to enrich for gametocytes will be done at two timepoints per individual to determine per-gametocyte infectivity and confirm whether PQ sterilizes gametocytes, followed by MFA. The primary outcome will be the reduction in mosquito infection rate within each arm at day 2 post-treatment. Secondary outcomes include within and between arm comparisons in other mosquito infection, gametocyte, safety, and biochemical parameters.

3. STUDY BACKGROUND AND RATIONALE

3.1. Background

Worldwide malaria morbidity and mortality remains unacceptably high, with an estimated 241 million cases in 2020, a substantial increase from 214 million in 2015 [7]. In addition to this, the emergence and spread of resistance to first-line drugs is threatening to further increase this rise in malaria cases and deaths. Therefore, there is a clear need for interventions that reduce malaria transmission.

Artemisinin combination-based therapies (ACTs) are the first-line treatment for uncomplicated *P. falciparum* malaria; however, they have very limited activity against mature gametocytes, the stages responsible for transmission to the mosquito. The 8-aminoquinolone primaquine is a potent and fast-acting gametocytocidal drug and is currently the only drug recommended for blocking malaria transmission. To reduce *P. falciparum* transmission, the World Health Organisation (WHO) recommends the addition of a single low dose of primaquine (SLD PQ) (0.25 mg/kg), to ACT. The benefit of adding SLD PQ has been assessed with Dihydroartemisinin-Piperaquine (DP), Pyronaridine-Artesunate (PA) and Artemether-Lumefantrine (AL), concluding effective blockage of transmission within 48 hours [3], [8] [NECTAR3, in preparation]. However, the added benefit of combining PQ with Artesunate-Amodiaquine (ASAQ) has not yet been tested, despite ASAQ being the first-line ACT in many countries [7]. Importantly, an individual-level meta-analysis of gametocyte data before and after ACT treatment suggested that ASAQ may be inefficient in clearing gametocytes with a fourfold higher odds of gametocyte carriage compared to the most widely used ACT that is AL [2].

The stagnation of progress toward reducing global malaria morbidity and mortality may be compounded by the emergence of artemisinin resistance. Artemisinin resistance, characterized by slow parasite clearance [9], [10] because of reduced susceptibility of ring-stage parasites [11], first emerged in Southeast Asia, a region that has been the epicentre for resistance development against all the major anti-malaria drugs in the past. In many areas with artemisinin resistance, resistance to the partner drug has now emerged as well, leading to a rapid rise in treatment failures following ACT [12], [13].

Artemisinin resistance is mediated by mutations in the propeller region of the *Kelch 13* (K13) gene. Recently, K13 mutations and associated delayed clearance of parasites have been found in East-Africa as well [14], [15]. Wider spread of artemisinin resistance across the African continent, which bears the vast majority of the global malaria burden, could be disastrous. In order to avert a public health emergency, there is an urgent need for alternative treatments with combinations of existing drugs that could be deployed rapidly. Triple Artemisinin-based Combination Therapies (TACT), which combine an existing ACT with a second partner drug that is slowly eliminated, could be part of such an approach.

The rationale for TACT is similar to the one underlying ACT. By combining drugs with different treatment targets and/or resistance mechanisms, the probability that resistance will emerge to the combination is very low (i.e., the product of the probabilities for each individual drug). TACT could counteract resistance emergence and provide efficacious treatment against drug resistant infections. Artemether-Lumefantrine with Amodiaquine (ALAQ) is one such TACT and has been proven a safe, well-tolerated and efficacious treatment for uncomplicated *P. falciparum* malaria, including in areas with artemisinin and partner-drug resistance [5], [6]. The effect of ALAQ on mature gametocytes and infectivity is unknown, as well as the added benefit of combining PQ with ALAQ. Given that a major rationale for using TACT is a reduction in the transmission of artemisinin resistance, it is pressing to understand the impact of TACT on gametocyte production and infectivity.

3.2. Rationale

Artesunate-Amodiaquine (ASAQ) is a commonly used ACT, however, its transmission reducing efficacy remains largely unknown. Studies microscopically assessing gametocyte carriage post-ASAQ treatment reached very different conclusions, ranging from increased

gametocyte carriage until day 3 [16] or day 7 [17] post-treatment to an immediate decrease in gametocytaemia [18]. Compared to AL, ASAQ appears to be less efficient in preventing post-treatment gametocyte carriage [2]. In addition, it is important to note that gametocyte carriage is a poor measurement for human-to-mosquito transmission, as antimalarial drugs can sterilise gametocytes before removing them from the blood stream [19] and transmissible gametocytes can persist at submicroscopic densities [20]. Membrane feeding assays (MFA) are therefore the most reliable method to assess transmission. MFA can be supported by magnetic enrichment of gametocytes that can allow for assessments of infectivity of increased gametocyte densities [21] and differentiate between lack of infectivity because of gametocyte densities that are too low to permit transmission and gametocyte sterilization [22]. This is relevant since uncertainties remain about the exact working mechanism of transmission-blocking antimalarial drugs that may clear gametocytes, distort their sex-ratio or sterilize gametocytes without clearance from circulation [19]. Understanding the mode by which transmission is prevented can support drug development.

Only one study has performed MFA after ASAQ treatment, reporting an increase in transmission [17]. If there is indeed substantial transmission after treatment with ASAQ, the addition of a single low dose PQ may be considered. To date, the added benefit of PQ when used in combination with ASAQ is unknown.

We previously showed that Artemether-Lumefantrine (AL) is a more potent ACT in terms of gametocyte clearance and transmission reduction efficacy compared to Dihydroartemisinin-Piperaquine (DP) [3], [4], [NECTAR3, in preparation]. It is currently unclear what the reason is for this marked difference and whether gametocyte-sterilization plays a role or the effect is driven by gametocyte-clearance. Recently, triple artemisinin-based combination therapies (TACT) such as Artemether-Lumefantrine plus Amodiaquine (ALAQ), which combine an existing ACT with a second partner drug that is slowly eliminated, have been proposed to provide efficacious treatment for multidrug-resistant *P. falciparum* infections and to delay the emergence of drug resistance [5], [6]. The transmission reducing efficacy of ALAQ or ALAQ combined with a single dose of PQ has not yet been tested.

Therefore, we propose to conduct a five-arm, phase 2, single-blind, randomised control trial to test the gametocytocidal and transmission-blocking efficacy of SLD PQ in combination with Artesunate-Amodiaquine and Artemether-Lumefantrine-Amodiaquine. Individuals will be recruited to an AL only arm as an internal control for the ALAQ arm, and for comparison to recent trial [NECTAR3, in prep]. Individuals who meet inclusion criteria will be randomised in a 1:1:1:1:1 ratio to: ASAQ, ASAQ-PQ, AL, ALAQ, ALAQ-PQ.

4. OBJECTIVES

4.1. Primary specific objective

To assess the within-person reduction of infectivity of gametocytes following administration of ASAQ alone or with single-dose PQ and AL alone or with AQ and ALAQ alone or with single-dose PQ in children and adults at day 2 post-treatment compared to pre-treatment (day 0).

4.2. Secondary specific objectives

- To assess differences in other mosquito infectivity parameters (mosquito infection rate, change in infection rate, infectivity to mosquitoes, and oocyst density) following treatment with ASAQ, ASAQ-PQ, AL, ALAQ and ALAQ-PQ in children and adults at all feeding timepoints compared to pre-treatment (day 0) and between treatment matched arms (ASAQ vs ASAQ-PQ, AL vs ALAQ, ALAQ vs ALAQ-PQ).
- To assess differences in gametocyte parameters (prevalence, density, circulation time, area-under-the-curve, sex-ratio) following treatment with ASAQ, ASAQ-PQ, AL, ALAQ and ALAQ-PQ in children and adults at all feeding timepoints compared to pre-treatment (day 0) and between treatment matched arms (ASAQ vs ASAQ-PQ, AL vs ALAQ, ALAQ vs ALAQ-PQ).
- To assess differences in safety parameters (AE frequency, Hb density, median drop in Hb) following treatment with ASAQ, ASAQ-PQ, AL, ALAQ and ALAQ-PQ in children and adults at all feeding timepoints compared to pre-treatment (day 0) and between treatment matched arms (ASAQ vs ASAQ-PQ, AL vs ALAQ, ALAQ vs ALAQ-PQ).
- To assess differences in biochemical parameters (ALT, CBC, Creatinine) following treatment with ASAQ, ASAQ-PQ, AL, ALAQ and ALAQ-PQ in children and adults at all feeding timepoints compared to pre-treatment (day 0) and between treatment matched arms (ASAQ vs ASAQ-PQ, AL vs ALAQ, ALAQ vs ALAQ-PQ).

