7.2. Secondary outcome measures

- Median within person percent change (presented as percent reduction) in mosquito infection rate from baseline to all feeding time-points, with comparison within and between arms.
- Median mosquito infection rate at all feeding time-points, with comparison within treatment arms compared to baseline, and between arms.
- Infectivity to mosquitoes at all feeding time-points, with comparison within treatment arms compared to baseline, and between arms.
- Mean oocyst intensity (in all/all infected mosquitoes) at all feeding time-points, with comparison within treatment arms compared to baseline, and between arms.
- Male and female gametocyte prevalence at all time-points, determined by microscopy or molecular assays, with comparison within treatment arms compared to baseline, and between arms.
- Male and female gametocyte density at all time-points, determined by microscopy or molecular assays, with comparison within treatment arms compared to baseline, and between arms.
- Male and female gametocyte sex ratio (proportion male) at all time-points, determined by microscopy or molecular assays, with comparison within treatment arms compared to baseline, and between arms.
- Gametocyte circulation time (cumulative), determined by microscopy or molecular assays, compared between treatment arms.
- Gametocyte area under the curve (cumulative), determined by microscopy or molecular assays, compared between treatment arms.
- Asexual and total parasite prevalence at all time-points, determined by microscopy or molecular assays, with comparison within treatment arms compared to baseline, and between arms.
- Asexual and total parasite density at all time-points, determined by microscopy or molecular assays, with comparison within treatment arms compared to baseline, and between arms.
- Haemoglobin density at all time-points, with comparison within treatment arms compared to baseline, and between arms.
- Median within person percent change (presented as percent reduction) in haemoglobin density from baseline to all time-points, with comparison within and between arms.
- The frequency and prevalence of adverse events (all AE's, treatment related AE's, and haematological AE's) observed up to and including day 2, 7, and 14 post-treatment, and at all timepoints.

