7.3. Exploratory outcomes

- Parasite genotype and transcriptional analysis at baseline and at post-treatment timepoints, both for blood stage parasites and oocysts.
- Plasma biomarkers (antibodies and parasite protein) at baseline and at post-treatment timepoints.
- Association between gametocyte density and mosquito infection rates per study drug and time-point, to examine evidence for loss in gametocyte fitness/sterilization.
- Human genotype analysis at baseline (G6PD, CYP2D6, HBB)
- ALT/Creatine density at all time-points with comparison within treatment arms compared to baseline, and between arms.
- Gametocyte density, mosquito infection rate and mean oocyst intensity before and after MACS, for within treatment arm comparison to baseline and comparison between treatment arms.

Table 5. Outcome measures

Outcome measure	Day 0	Day 1	Day 2	Day 7	Day 14	Day 21	Day 28
Mosquito infectivity	*		*	*	*	**	**
Asexual parasite prevalence & density	*		*	*	*	*	*
Gametocyte prevalence, density, sex ratio, genotype	*		*	*	*	*	*
Biochemistry (ALT/Creatinine)	*		*		*		
CBC	*		*		*		
Haemoglobin	*	*	*	*	*	*	*
Safety assessment: signs of haemolysis	*	*	*	*	*	*	*
Safety assessment: Adverse Events	*	*	*	*	*	*	*
Plasma biomarkers	*		*	*	*	*	*
Mosquito infectivity after MACS	*		*				

** Mosquito infectivity assays will be performed at day 21 for any individuals infectious at day 7 or 14; and at day 28 for any individuals infectious at day 14 or 21.

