9. SAFETY EVALUATION

The major safety endpoint is haemolysis. For this reason, haemoglobin will be measured before treatment, at days 1, 2, 7, 14, 21, and 28. Previous studies have shown that highest haemoglobin fall related to drug induced haemolysis can be detected within 7 days after treatment. In addition at 24 hours, and subsequent days of follow up, a questionnaire

assessing adverse events (AE) will be carried out. All participants will have access to contact study medical staff 24 hours a day and medical facilities that can give safe blood transfusions. Participants who require blood transfusions will be hospitalised at the district hospital in Ouelessebougou or referred to the University hospitals in Bamako for proper management. Additional safety precautions due to the small risk of transient haemolysis in this population will include the performance of clinical examinations and monitoring for adverse events (AE) at all sampling time points, carefree of charge to all participants throughout the duration of follow-up.

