9.1. Definitions

9.1.1. Adverse events

Adverse events are defined as any undesirable experience occurring to a subject during the study, whether or not considered related to trial. An AE can therefore be any unfavourable and unintended sign (including an abnormal laboratory finding), symptom, or disease (new or exacerbated) temporally associated with a study intervention. AEs may include events that occur as a result of protocol-mandated procedures (i.e. invasive procedures). All AEs reported spontaneously by the subject or observed by the trial clinicians, or their staff will be recorded. Abnormal laboratory findings or other abnormal assessments that are judged by the trial clinicians to be clinically significant will be recorded as AEs or serious adverse events (SAEs) if they meet the definition. The investigators and trial clinicians will exercise their medical and scientific judgement in deciding whether an abnormal laboratory finding, or other abnormal assessment is clinically significant.

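### Objective 4.2 compares adverse event frequency with pre-treatment day 0, a near-empty reference that tilts the within-arm contrast towards an increase and cannot inform on drug safety

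*Protocol*

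**What the plan says.** - **Objective (Protocol 4.2).** The third bullet is "To assess differences in safety parameters (AE frequency, Hb density, median drop in Hb) following treatment with ASAQ" and the other four regimens. The comparator is "at all feeding timepoints compared to pre-treatment (day 0) and between treatment matched arms". All four secondary objectives share that wording.
- **Outcome (Protocol 7.2).** AE frequency and prevalence are those "observed up to and including day 2, 7, and 14 post-treatment, and at all timepoints". This bullet names no comparator. The haemoglobin bullets just above it do name baseline.
- **Definition (Protocol 9.1.1).** AEs are undesirable experiences during the study, and the text goes on to describe a sign, "symptom, or disease (new or exacerbated) temporally associated with a study intervention".
- **Collection (Protocol 9 and Table 5).** Section 9 says "In addition at 24 hours, and subsequent days of follow up, a questionnaire" on AEs is administered. The same section requires "monitoring for adverse events (AE) at all sampling time points", and the row "Safety assessment: Adverse Events" in Table 5 is marked at all seven visits, day 0 included.
- **Entry (Protocol 5.5 and 5.6).** Fever-defined symptomatic malaria and signs of acute or chronic illness are excluded.
- **Analysis (Protocol 11.1).** No test is named for AEs. Remaining quantitative data go to signed-rank tests against day 0 and rank-sum tests between matched arms, with significance at p < 0.05.

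**The concern.** Haemoglobin has a measured value before dosing, so its change from day 0 means something. An AE is an event that needs time at risk, and before the first dose there is little of it and no drug exposure. Objective 4.2 nevertheless makes day 0 the within-arm reference for AE frequency. It is the only place in the protocol that specifies any AE comparison.

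Followed as written, it sets a near-zero pre-dose figure against counts that build up over 2, 7, 14 and finally 28 days. The difference would reflect when AE counting begins and how long it runs, mixed with background illness, procedures and drug effect in unknown shares. A reader could take a significant within-arm rise as a safety signal for a regimen when it carries no such information.

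**Working it through.** The protocol gives no figure for this comparison, so there is none to reproduce. The calculations below are illustrations.

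**Inputs**
- n = 20 per arm (Protocol 5, Table 1).
- Significance at p < 0.05 (11.1), read as two-sided (assumption).
- A post-treatment AE proportion of about 30%, which 12.2.1 gives for artesunate-amodiaquine only. Values of 5%, 10% and 20% are assumed to show the range.
- Day-0 count of 0 (assumption, relaxed in step 4).

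**1. Direction.** With a day-0 count of 0, no decrease is possible. P(tie) = (1 − p)^20 and P(increase) = 1 − (1 − p)^20.

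**2. Significance under an exact paired test.** If k participants have an AE later and none at day 0, the exact two-sided McNemar p is 2 × 0.5^k. For k = 5 this is 0.0625 and for k = 6 it is 0.031, so six are needed. The protocol does not name this test.

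| Later AE proportion | P(any increase) | P(tie) | P(6 or more of 20) |
|---|---|---|---|
| 5% | 0.6415 | 0.3585 | 0.0003 |
| 10% | 0.8784 | 0.1216 | 0.0113 |
| 20% | 0.9885 | 0.0115 | 0.1958 |
| 30% | 0.9992 | 0.0008 | 0.5836 |

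If AE counts instead fell under the signed-rank default of 11.1, with one AE per affected participant, z = √k. Four participants would then suffice (z = 2, p = 0.046). P(4 or more) is 0.59 at 20% and 0.89 at 30%.

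**3. Window length.** Suppose a constant background rate, unrelated to treatment, that gives 5% with an AE by day 2. The cumulative proportion by day t is 1 − 0.95^(t/2):
- day 7: 1 − 0.95^3.5 = 16.4%
- day 14: 1 − 0.95^7 = 30.2%
- day 28: 1 − 0.95^14 = 51.2%

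The contrast with day 0 grows about tenfold while the underlying rate does not change.

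**4. Day-0 events present.** Table 5 schedules AE assessment on day 0, so take an assumed 5% day-0 prevalence and treat the two counts as independent binomials:
- later prevalence 5%: increase 0.345, tie 0.310, decrease 0.345
- later prevalence 30%: increase 0.979, tie 0.015, decrease 0.006

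The direction is then no longer fixed.

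**5. All five arms.** At a 30% rate in every arm (an assumption beyond 12.2.1), the McNemar probabilities give at least one significant arm with probability 1 − (1 − 0.584)^5 = 0.99. All five are significant with probability 0.584^5 = 0.07. At 20% the figures are 1 − (1 − 0.196)^5 = 0.66 and 0.196^5 = 0.0003.

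**The case against.** The strongest reply is that the day-0 phrase is shared template wording, meant to apply only where it fits. The gametocyte objective attaches it to circulation time and area under the curve, which have no day-0 value and which 7.2 compares between arms only. The AE bullet in 7.2 likewise names no baseline comparison. The synopsis says only "Secondary outcomes include within and between arm comparisons in other mosquito infection, gametocyte, safety, and biochemical parameters", without mentioning AEs or day 0. The valid randomised comparison already stands in the same sentence of 4.2, and no primary endpoint, sample size or stopping rule depends on the day-0 contrast.

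Much of this stands, and it limits the consequence. It does not remove the defect. The AE bullet in 7.2 names no comparator at all, within or between arms, so 4.2 is the only specification and it includes day 0.

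A reader might go further and infer that every within-arm AE comparison must show an increase, or that all arms would show significant ones even for an inert regimen. The documents do not support that:
- Table 5 and section 9 schedule AE assessment on day 0 as well, so the start of collection is inconsistent, not settled at 24 hours.
- Entry does not require absence of all symptoms. Symptomatic malaria is defined by fever, mild complaints are not expressly excluded, and paracetamol and aspirin are allowed (5.6).
- Some on-study time before dosing exists, since screening follows consent and procedure-related events count as AEs (9.1.1).
- Ties are possible with a zero day-0 count, and decreases are possible otherwise.
- Significance in all five arms has a probability of only about 7% even at a 30% rate.

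**Conclusion.** The concern holds in limited form. Objective 4.2 sets AE frequency against a reference that is near zero or undefined, while 7.2 accumulates the later counts. The within-arm contrast is tilted towards an increase whatever the cause of the events and says nothing usable about drug safety. The tilt is strong at AE proportions of 20% to 30% and weaker at 5%, where a zero day-0 count gives a tie in 36% of arms. It is not a certainty in every arm.

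The figures assume 20 per arm, a day-0 count of 0 unless stated, and tests that the protocol does not specify for AEs. The 30% figure comes from the protocol for one regimen only. The conclusion about direction rests on the definitions and the schedule, not on these rates.

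The comparison between matched randomised arms is unaffected. This is a wording correction worth making, with modest consequences if missed.

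**What to change.** - **Protocol 4.2:** take AE frequency out of the day-0 comparison and keep that comparison for haemoglobin.
- **Protocol 4.2 and 7.2:** state that AEs are compared between the matched randomised arms (ASAQ vs ASAQ-PQ, AL vs ALAQ, ALAQ vs ALAQ-PQ) over the same cumulative windows, to days 2, 7 and 14 and over the whole 28-day follow-up.
- **Day 0:** use symptoms recorded then only as a baseline for judging whether a later event is new or worse.
- **Section 9 and Table 5:** reconcile the questionnaire starting at 24 hours with the AE mark at day 0, and say what is recorded at that visit.

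The effect measure and interval method can be left to the statistical analysis plan. The cost is a few sentences. No data, visits or sample size change, and only an uninterpretable set of comparisons is lost.
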